8.2 Adverse Event Reporting

8.2.1 Reporting Adverse Events to Sponsor/Designee

During the course of the study, the Investigator or designee will routinely monitor each subject for the occurrence of any AE/ADE. If an AE/ADE occurs, the Investigator or designee will complete the AE eCRF which includes the following:

- Description of the event
- Start and stop date of the event
- Timing of the event (prior to first study treatment, during treatment set-up, during treatment, within 4 hours after treatment ends, > 4 hours after treatment ends)

[figure not shown]

- Seriousness of the event (yes, no) (assessed by PI or Sub-I)
- Severity of the event (mild, moderate, or severe) (assessed by PI or Sub-I)
- Causality of the event (related to treatment and/or related to the device) (assessed by PI or Sub-I)
- Action taken
- Outcome of the event (fatal, not recovered/not resolved, recovered/resolved with sequelae, recovered/resolved, and unknown)

All SAEs must be reported to the Sponsor/designee within 24 hours of the Investigator or designee becoming aware of its occurrence. The informed site team member should also contact their site monitor by phone or email to notify him/her of the event. This requirement is irrespective of whether the AE is thought to be possibly related to the study product or not. Expedited Reporting of Serious Adverse Events and Suspected Unexpected Serious Adverse Reaction (SUSAR). Sponsor/designee will assess each SAE reported by the Investigator to determine if the SAE qualifies as an expedited report according to FDA criteria. Sponsor/designee will report to FDA according to the applicable time requirements.

Per regulations, when an Unexpected Adverse Device Effect (UADE) or SUSAR occurs Investigators will receive a letter from Sponsor/designee describing the UADE/SUSAR. The Investigator should file this letter within their Investigator Study Binder. Additionally, the expedited report letter should be submitted by the Investigator to their IRB/REB, as appropriate per FDA regulations.

8.2.2 Device-Related Product Complaints

8.2.3 Trial Subject Reporting – Product Issues

Throughout the trial, HemoCareTM Hemodialysis System will record and report device alarms. The alarm time(s), code(s), and description(s) will be reported to the Sponsor as

they occur via HemoCareTM Connectivity Platform. This data will be maintained for end of study statistical analysis. Additionally, this data will be reviewed and trended by the Sponsor and/or designee for safety concerns or service requirements. In addition to device reported product issues, trial sites will also report product issues.

During both Evaluable Periods (Assisted & Unassisted), trial subjects or care partners will be instructed to contact the on-call study site staff for any product issues which cannot be resolved using the User Manual or training tools. The site staff will assist the subject in resolving the product issue using the device User Manual and training material. If the site is unable to resolve the product issue, they will be instructed to contact the Sponsor/designee for device support. The site staff will also contact the Investigator or designee to discuss next steps for the trial subject in the event of an incomplete or missed treatment.

8.3 Clinical Laboratory Tests

8.3.1 Laboratory Parameters

A central laboratory will perform laboratory tests for hematology and serum chemistries.

With exception, sites may use and will be encouraged to use their local laboratory for activated partial thromboplastin time (aPTT) measurements if using the central laboratory may confound results based on the potential shipping timelines (e.g., local weather, sample collection time point).

Subjects will be in a seated or supine position during blood collection. List of clinical laboratory tests is found below.

List of Laboratory Tests:

Serum Chemistry:

- Comprehensive metabolic panel (including glucose, calcium, sodium, potassium, total carbon dioxide or serum bicarbonate, chloride, urea, creatinine, ALP, ALT, AST, total bilirubin, serum albumin, and total protein + serum phosphorous (pre-dialysis))
- Iron profile (pre-dialysis)

Hematology:

• CBC (pre-dialysis)

Coagulation:

 Activated partial thromboplastin time (aPTT)

CBC=complete blood count; ALP=alkaline phosphatase; ALT=alanine amino transferase; AST=aspartate amino transferase; aPTT=activated partial thromboplastin time

The Investigator will receive the laboratory results for review and signature. The Investigator will be notified of any laboratory value that is outside of the normal range, as defined by the central laboratory and included as part of the laboratory manual. If a clinically meaningful change from Screening or the previous visit occurs for any laboratory value and results in medical intervention, as judged by the Investigator, the laboratory abnormality will be recorded as an AE on the eCRF.

8.3.2 Sample Collection, Storage and Shipping

A study specific Laboratory Manual will be provided by the central laboratory to the Investigators and will include detailed instructions on the collection, preparation, storage, and shipping procedures for blood samples and the appropriate laboratory ranges. If a local laboratory is used for aPTT testing, the local laboratory will be required to provide kits and instructions to Investigators.

Depending on site staff availability, an in-home nurse or technician service may be utilized to collect, process, and ship samples which must be collected during the home period. The in-home nurses selected for this activity will be qualified in sample collection, processing, packaging, and shipping. Use of in-home nurses will minimize sampling errors and maximize consistency. During the in-center periods, the sites will be required to provide qualified nurses for sample collection, processing, packaging, and shipping.

9 Statistical Considerations

9.1 General Considerations

Further details of the planned statistical methods presented below will be provided in the study statistical analysis plan (SAP). The purpose of the SAP is to further elaborate the statistical methods described in the protocol and describe analysis conventions to guide the statistical programming work. Any changes to the final SAP will be documented. Unless otherwise specified, treatment effects will be evaluated based on a 2-sided significance level of 0.050 (when rounded to 3 decimal places)

9.2 Determination of Sample Size

The goal is to have at least 1000 HemoCare™ treatments in both Evaluable Periods, in agreement with the FDA, to make a *clinical determination* of the safety of HemoCare™ based on the rate and type (i.e., device related) of AEs documented. To achieve this goal, at least 30 subjects will enter the Assisted Evaluable Period. No more than 25% of the total study subjects who complete the study may be enrolled at one site. Assuming each Evaluable Period is 3.5 treatments per week (one treatment every other night), each patient is expected to contribute 34 treatments to each Evaluable Period and 68 evaluable treatments to the study.

Based upon the number of treatments and the expected rate of adverse events, the current study design is under-powered to detect a clinically meaningful (less than 10%) non-inferiority margin for the Unassisted Evaluable Period.

For the primary performance endpoint, 'success' is defined as a subject who has all stdKt/Vurea measures in an evaluable period greater than or equal to 2.0. Several sets of simulation samples were generated (2,000 samples per set) assuming a rate of success between 95% and 99.5% for the Assisted Evaluable Period treatments paired with some fewer successes for the Unassisted Evaluable Period treatments. The success rate of the 2 periods were compared and the CI interval for the differences were calculated. With 30 subjects in each Evaluable Period, a margin of 10% will provide 91% power to declare non-inferiority if the actual success rate is 99% and 83% power if the actual success rate is 98%.

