- Number of anticipated and unanticipated AEs and SAEs during each Evaluable Period including number of devicerelated AEs and SAEs.
- 2. Incidences of decreased and increased post-dialysis serum phosphorus during each Evaluable Period.
- Incidences of decreased and increased post-dialysis serum potassium during each Evaluable Period.
- 4. A descriptive summary of UF and target weight during each Evaluable Period.

Exploratory Endpoints:

- Reliability of HemoCare™ Hemodialysis System for the provision of treatments as scheduled and the ability to deliver prescribed treatments.
- Proportion of subjects and care partners who successfully complete training with HemoCare™ Hemodialysis System and enter the Unassisted Home Evaluable Period.
- 3. Subjects' scores for Patient Recovery Time Questionnaire, Renal Treatment Satisfaction Questionnaire (RTSQ) and Care Partner scores for Zarit Burden Interview 12 item version (ZBI-12).

	4. A descriptive summary by Evaluable Period of the total number of alarms, type of alarms and the time to resolve alarms will be provided.
Study Population:	Up to 70 subjects receiving HD may be enrolled in this study in order to achieve approximately 30 subjects entering the Unassisted Home Evaluable Period. No more than 25% of the total study subjects who complete the study may be enrolled at one site.
Study Duration:	Duration of Study participation will be documented by the Subject's active participation which is expected to be a minimum of 34 treatments per Evaluable Period.
Study Design and Methodology:	This is a prospective, multi-center, open-label, single-arm, cross-over study.
	A written informed consent will be obtained from each subject and care partner before starting any study related procedures. Subjects will undergo screening for eligibility during which inclusion and exclusion criteria will be evaluated. The screening period will be up to 30 days prior to enrollment.
	Eligible subjects will enter In-Facility Introduction Period during which they will begin training at the study site. This period will last approximately 1 to 6 weeks, but may be extended up to 12 weeks at the Investigator's discretion. The subjects will receive professionally attended Hemodialysis (HD) treatment with HemoCare TM Hemodialysis System at least 3 times every seven days. The duration of each HD treatment will be determined by the clinician on a case by case basis.

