5.3 Subject Discontinuation/Withdrawal

Subjects may be withdrawn/prematurely discontinued from the study if their participation is discontinued before completion of the Unassisted Evaluation Period. The reason(s) could include:

- 1. Adverse event(s) (AEs)
- Inadequate dialysis
- 3. Protocol violations (i.e., the subject failed to meet protocol entry criteria or did not adhere to the protocol requirements)
- 4. Pregnancy, lactating or not using medically acceptable means of contraception (confirmed by Investigator)
- 5. Lost to follow-up (i.e., subject fails to return for study visits)
- 6. Voluntary withdrawal (i.e., subject's request)

- 7. Termination of the study
- 8. Investigator's discretion
- 9. Renal transplantation
- 10. Switch to Peritoneal Dialysis (PD)
- 11. Subject death
- 12. Other reason (with reason noted on the electronic case report form [eCRF])

The Investigator may terminate a subject's study participation at any time during the study if he/she judges it to be in the subject's best interest. In addition, a subject may discontinue his or her participation at any time during the study. If a subject's participation is discontinued, the reason(s) must be recorded in the source documents and on the eCRFs. If a subject discontinues for any reason, every effort should be made to perform all of the procedures that are scheduled for the last visit. In addition, adverse device effects (ADEs) and all serious adverse events (SAEs), related to study treatment or not, will be followed post-study by the Investigator until the subject is stable or the situation is resolved.

Discontinued subjects will not be replaced unless the targets for enrollment/treatments will not be achieved with the current active group of study subjects. The Investigator or designee should inform their site monitor the moment any subject is discontinued from the study.

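### The sample size is anchored on the Assisted Period in two places and on the Unassisted Period in a third, with no attrition allowance; and the stated 91%/83% power is not what the continuity-corrected analysis in 9.4.2 gives at 30 per period

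*Combined protocol and SAP*

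**What the plan says.** Three places in the protocol set the number of subjects.

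- Section 9.2 gives the treatment goal, "The goal is to have at least 1000 HemoCare™ treatments in both Evaluable Periods", and says it is met because "at least 30 subjects will enter the Assisted Evaluable Period". It counts 34 treatments per subject per period.
- The synopsis, Statistical Considerations, repeats the Assisted Period anchor and makes 34 a minimum.
- The synopsis, Study Population, uses the other period: "Up to 70 subjects receiving HD may be enrolled in this study", "in order to achieve approximately 30 subjects entering the Unassisted Home Evaluable Period".

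The power statement in 9.2 needs 30 in both periods: "With 30 subjects in each Evaluable Period, a margin of 10% will provide 91% power to declare non-inferiority" at 99% success, and 83% at 98%. Section 9.4.2 analyses performance on the per-protocol (PP) set, which 9.3 restricts to subjects with at least 34 treatments in each period. The method in 9.4.2 is an independent-sample risk difference with continuity correction, a two-sided 90% interval and a margin of 0.10.

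On replacement, 5.3 says: "Discontinued subjects will not be replaced unless the targets for enrollment/treatments will not be achieved with the current active group of study subjects".

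**The concern.** Entry to the Assisted Period and entry to the Unassisted Period are different targets once anyone leaves between them. The protocol expects some to leave: 5.3 lists reasons for discontinuation, subjects must be certified before treating without a professional, and the proportion entering the Unassisted Period is itself an exploratory endpoint.

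At stake is the Unassisted treatment count. Section 9.2 describes the 1,000-treatment goal as agreed with the FDA for a clinical judgement of safety, and concedes that the formal safety comparison is under-powered, so the count carries much of the safety case. The performance conclusion also rests on a power figure tied to 30 subjects in each period and to an interval method that should be the one planned.

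**Working it through.** **Inputs.** Goal of 1,000 treatments, taken as 1,000 in each period; 34 treatments per subject per period; 30 subjects; power of 91%/83% at 99%/98% success (all Section 9.2). Margin 0.10, two-sided 90% interval, continuity correction (9.4.2). PP rule of 34 in each period (9.3). Cap of 70 (synopsis).

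**The plan's own number.** 1,000 / 34 = 29.4, rounded up to 30. The stated 30 is reproduced. 30 × 34 = 1,020, a reserve of 20 treatments.

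**Losses before the Unassisted Period, at exactly 34 treatments each.** One loss: 29 × 34 = 986. Two: 28 × 34 = 952. Three: 27 × 34 = 918.

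**Losses during the Unassisted Period.** A subject who leaves after 14 treatments still brings the total to 986 + 14 = 1,000. Twenty-nine subjects averaging 1,000 / 29 = 34.5 also reach it. For the PP set, however, leaving at any time before the 34th Unassisted treatment takes 30 down to 29.

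**Assisted entry needed for 30 to enter Unassisted.** N = 30 / (1 − d), rounded up. The documents give no attrition rate, so d is an assumption.

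| d | N entering Assisted |
|---|---|
| 5% | 32 |
| 10% | 34 |
| 15% | 36 |
| 20% | 38 |
| 30% | 43 |

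All lie under the cap of 70.

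**Power at 30 per period.** Take the upper bound as (p1 − p2) + 1.645 × √[p1(1 − p1)/n + p2(1 − p2)/n], plus 1/n when the correction is applied, and require it to be below 0.10. Enumerate all pairs of binomial outcomes with equal true rates.

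A single Unassisted failure with no Assisted failure shows what the correction does at n = 30. The difference is 1/30 = 0.033 and the standard error is √[(1/30)(29/30)/30] = 0.0328. The uncorrected bound is 0.033 + 1.645 × 0.0328 = 0.087, which passes. The corrected bound is 0.087 + 0.033 = 0.121, which fails. One failure in each period also fails after correction (0.076 + 0.033 = 0.110). Success therefore depends almost entirely on having no Unassisted failure, which has probability 0.99^30 = 0.740 or 0.98^30 = 0.545. The few remaining passing outcomes bring these to the totals below.

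| n per period | Uncorrected, 99% / 98% | Corrected, 99% / 98% |
|---|---|---|
| 30 | 96.4% / 88.2% | 74.8% / 58.6% |
| 29 | 96.6% / 88.8% | 75.5% / 59.4% |
| 27 | 97.0% / 90.0% | 76.3% / 58.5% |
| 26 | 81.7% / 72.1% | 77.0% / 59.6% |
| 24 | 82.7% / 73.2% | 78.6% / 61.9% |

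The stated 91%/83% lies between the two columns at n = 30. Newcombe and score intervals give about 75%/59%, Agresti-Caffo 79.8%/69.9%, a paired Wald interval 96.5%/88.5% and the normal approximation 98.8%/86.9%. None comes within 2 points of both stated figures. Setting the Assisted rate to 100% and the Unassisted rate to 99% or 98% gives 74.0%/54.5% with the correction.

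**The case against.** The strongest reply is that the two anchors can both be met. At least 30 is a floor, and getting about 30 into the Unassisted Period already means that at least about 30 entered Assisted. Enrolling up to 70 to obtain about 30 is an allowance for losses. Section 5.3 permits replacement when the treatment target would be missed, and that target is worded consistently; a projected 986 would trigger it. Thirty-four is a minimum, and a Device Holiday can extend participation to complete the required treatments.

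Much of this stands, and it rules out three stronger readings that a reader might infer.

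- That any drop-out misses 1,000 treatments. It does not: an exit after 14 or more Unassisted treatments, or slightly more than 34 treatments from the others, still reaches the goal.
- That the replacement clause cannot help. Only its enrolment target is ambiguous; its treatment target is not.
- That losing four subjects is what lowers power. The fall at 26 occurs only in the uncorrected Wald calculation, where one Unassisted failure gives a bound of 0.1005 against 0.10. It is a discreteness effect. With the planned correction, drop-out barely moves power, which is slightly higher at 24 than at 30.

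What the reply leaves untouched is that 9.2 presents 30 entering Assisted as sufficient without stating any loss between periods. The cap of 70 covers losses from enrolment onward and does not say how many must enter Assisted. The replacement clause also does not say that its enrolment target is the Unassisted one.

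On power, the simulation is not fully described, and its two descriptions differ: the synopsis assumes no difference between periods, while 9.2 pairs the Assisted rate with somewhat fewer Unassisted successes. The stated figures may therefore come from a setting that cannot be recovered. That is a reason to restate them, since the method they should describe is the one in 9.4.2.

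**Conclusion.** The point holds as an inconsistency in the sample-size target and a mismatch in the power statement. The target is stated two ways, and the synopsis disagrees with itself as well as with 9.2. At 30 entering Assisted and 34 treatments each, the reserve is 20 treatments; one loss before the Unassisted Period leaves 986 treatments, and any incomplete Unassisted Period leaves fewer than 30 in the PP set. The shortfall is avoidable under the existing rules, but 9.2 does not plan for it.

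Separately, and independently of drop-out, power at 30 per period under the planned correction is about 75%/59%, which is 16 and 24 points below the stated 91%/83%. Without the correction it is about 96%/88%.

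This rests on reading the goal as 1,000 in each period, which is what 30 × 34 implies; if 1,000 were a combined total, 30 subjects would give 2,040 and the count would not be at risk. It also rests on reading the correction as 1/n added to a Wald bound, with equal true rates and independent samples.

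**What to change.** 1. In 9.2 and in the synopsis Statistical Considerations, use the anchor already in the synopsis Study Population: about 30 subjects entering the Unassisted Period, within the cap of 70.
2. Give the number to enter Assisted with a stated attrition assumption, for example 34 at 10% or 38 at 20%.
3. Name the Unassisted anchor in 5.3 as the enrolment target that governs replacement.
4. Say that 1,000 treatments means 1,000 in each period, if that is the intent.
5. Restate power for the interval method in 9.4.2 and for the number expected in the PP set, with one description of the simulation shared by the synopsis and 9.2.

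The cost is protocol wording and a re-run of the simulation. Any added Assisted entries stay within the 70 already allowed. The restated power will probably be lower than the present figures.

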With an underlying goal to have at least 1000 HemoCareTM Hemodialysis System treatments in both Evaluable Periods, at least 30 subjects will enter the Assisted Evaluable Period. No more than 25% of the total study subjects who complete the study may be enrolled at one site. Each patient is expected to contribute at least 68 evaluable treatments to the study (at least 34 in each Evaluable Period).

Based upon the number of treatments and the expected rate of adverse events, the current study design is under-powered to detect a clinically meaningful (less than 10%) non-inferiority margin for the Unassisted Evaluable Period.

For the primary performance endpoint, 'success' is defined as a subject who has all stdKt/Vurea measures in an evaluable period greater than or equal to 2.0. Several sets of simulation samples were generated (2,000 samples per set) assuming a rate of success between 95% and 99.5% and no actual difference between the two Evaluable Treatment Periods. The success rate of the 2 periods were compared and the CI interval for the differences were calculated. With 30 subjects in each Evaluable Period, a margin of 10% will provide 91% power to declare non-inferiority if the actual success rate is 99% and 83% power if the actual success rate is 98%.

Analysis Populations:

The Intent-to-Treat (ITT) population set will include all subjects who have used HemoCareTM Hemodialysis System at least once during the Assisted Evaluable Period.

The Per Protocol (PP) population will include all subjects not having any enrollment violations and receiving at least 34 treatments in each Evaluable Period. The PP population will be used as sensitivity analyses of the primary safety endpoint and primary performance endpoint.

Poolability of the data will be examined by assessing the heterogeneity of the primary endpoint results across sites with 5 or more subjects enrolled.

Primary Safety Endpoint:

The AE rate per 100 HemoCare™ Hemodialysis System treatments of Unassisted Home Evaluable Period will be compared to that of the

Assisted Evaluable Period and a two-sided 90% CI will be generated for the rate ratio (λ_2/λ_1) comparing the relative difference in AEs for the two Evaluable Periods using a negative binomial regression model.

Primary Performance Endpoint:

Performance of the HemoCare™ Hemodialysis System will be assessed by weekly stdKt/Vurea that will be collected every two weeks during each Evaluable Period.

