9.4.2 Primary Performance Endpoint

Performance of HemoCareTM Hemodialysis System will be assessed by weekly stdKt/V_{urea} that will be collected every two weeks during each Evaluable Period. A successful weekly stdKt/V_{urea} is defined as a value of at least 2.0. If there is a retest of stdKt/V_{urea} for a

particular week (e.g., a missed or damaged sample) then the retested value will be used for analysis.

During each Evaluable Period, a binary outcome variable will be defined to be 1 if the weekly stdKt/Vurea for a given week meets the success criteria and 0 otherwise. For each subject, this will result in approximately 5 binary outcome values for each period. Each subject will be considered as meeting the primary performance endpoint for that period if all weekly stdKt/Vurea values meet the performance success criterion. A Non-inferiority test will be conducted. The difference in proportion of subjects (P1-P2) meeting the performance criteria in the Unassisted Evaluation Period (P2) and the Assisted Evaluation Period (P1) will be reported with a two-sided 90% CI.

$$H_0: p_1 - p_2 \ge \delta$$

 $H_1: p_1 - p_2 < \delta$

If the upper bound of the Confident interval is less than δ =0.10 then the null Hypothesis is rejected and non-inferiority is demonstrated.

The analysis will be carried out on the PP population. In addition, an analysis using the ITT population and the impact of missing data on the PP analysis will be explored as sensitivity analyses.

Multiple imputation (MI) will be used to assess the sensitivity of missing data on the ITT population. A MI logistic regression model for the efficacy success of each treatment-week will include the following factors: treatment, age, site, and weeks on home dialysis.

A risk difference analysis with continuity correction for independent samples will be performed. Although this will be paired rates, the independent sample analysis will be conducted because it is highly expected not having any failure, at least on the assisted treatment evaluable period.

The same analysis will be conducted using the PP population.

Furthermore, the impact of missing data on the primary analysis, will be explored as sensitivity analysis for both, ITT and PP population.

The evaluation of the primary performance endpoint will be based on the results from the PP population and the ITT population.

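### The stated 91% / 83% power for the primary performance endpoint does not match the interval named in section 9.4.2, and the synopsis and section 9.2 describe different simulations

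*Combined protocol and SAP*

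**What the plan says.** Section 9.2 and the sample-size part of the synopsis (section 1) give the same power for the primary performance endpoint. Taking 30 per period as the sample, they claim that "a margin of 10% will provide 91% power to declare non-inferiority if the actual success rate is 99% and 83% power" at a success rate of 98%. A subject succeeds in a period if every weekly stdKt/V measured in it is at least 2.0.

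On method, section 9.2 says only this: "The success rate of the 2 periods were compared and the CI interval for the differences were calculated". It does not identify the interval, any continuity correction, the within-subject correlation or the size of any true deficit. The two descriptions of the scenario differ. The synopsis has simulations "assuming a rate of success between 95% and 99.5% and no actual difference between the two Evaluable Treatment Periods". Section 9.2 has Assisted success rates "paired with some fewer successes for the Unassisted Evaluable Period treatments".

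Section 9.4.2 declares non-inferiority if the upper limit of a two-sided 90% CI for P1-P2 (Assisted minus Unassisted) is below 0.10. Of the primary analysis it says "The analysis will be carried out on the PP population". After the paragraph on multiple imputation in the ITT set it adds "A risk difference analysis with continuity correction for independent samples will be performed", explains "Although this will be paired rates, the independent sample analysis will be conducted because it is highly expected not having any failure", at least in the Assisted period, and continues "The same analysis will be conducted using the PP population". No other interval is named, and the form of the correction is not given. Section 9.1 defers further detail to an SAP.

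**The concern.** A stated power should belong to the analysis that will be run. With 30 subjects and success rates near 100%, the verdict turns on one or two failures, so a continuity correction of 1/30 or 1/60 can decide it. If the stated figures belong to a different interval or scenario, the risk of missing a primary endpoint when the two periods perform alike is understated. Leaving the correction open also leaves a pass/fail choice that could be made after the failures are known. Finally, a true Unassisted deficit lowers power, so the two described simulations would not be expected to give identical figures.

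**Working it through.** **Inputs.** n = 30 per period, success 99% or 98%, stated power 91% / 83% and 2,000 samples per set (synopsis, 9.2). Margin 0.10, two-sided 90% CI (z = 1.645), independent samples, continuity corrected (9.4.2). Assumptions: true difference 0, as the synopsis says; correlation 0 first, then 0 to 1; correction c = ½(1/30 + 1/30) = 1/30, or c = 1/(2×30) = 1/60, because the form is not stated.

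**Rule.** With x1 Assisted and x2 Unassisted failures and p̂ = 1 − x/30, the upper limit is

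U = (x2 − x1)/30 + 1.645·√[p̂1(1 − p̂1)/30 + p̂2(1 − p̂2)/30] + c, and the endpoint passes if U < 0.10.

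| x1, x2 | c = 0 | c = 1/60 | c = 1/30 |
|---|---|---|---|
| 0, 0 | 0.000 pass | 0.017 pass | 0.033 pass |
| 0, 1 | 0.087 pass | 0.104 fail | 0.121 fail |
| 1, 1 | 0.076 pass | 0.093 pass | 0.110 fail |
| 2, 1 | 0.059 pass | 0.076 pass | 0.092 pass |

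**Power, independent periods, no difference.** For 30 subjects, P(0 failures) = 0.7397 / 0.5455 and P(1 failure) = 0.2242 / 0.3340 at 99% / 98%. Outcomes with x2 = 0 pass. An outcome with x2 = 1 passes for any x1 if c = 0, for x1 ≥ 1 if c = 1/60, and for x1 ≥ 2 if c = 1/30. Outcomes with x2 ≥ 2 add at most 0.002.

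- c = 1/30: 0.7397 + 0.2242×0.0361 = **74.8%**; 0.5455 + 0.3340×0.1205 + 0.0003 = **58.6%**.
- c = 1/60: 0.7397 + 0.2242×0.2603 = **79.8%**; 0.5455 + 0.3340×0.4545 + 0.0003 = **69.8%**. A Hauck-Anderson correction gives the same.
- c = 0: **96.4%** / **88.2%**.

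None of these is 91% / 83%. The simulation error is too small to explain it: the 95% half-width with 2,000 samples is 1.96·√(0.91×0.09/2000) = 1.3 points, and 1.6 points at 83%.

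**Correlation between periods** (exact multinomial over each subject's 2×2 table, no difference; power at 99% / 98%):

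| Correlation | Named, 1/30 | Named, 1/60 | Paired Wald + 1/30 (not named) |
|---|---|---|---|
| 0 | 74.8 / 58.6 | 79.8 / 69.8 | 75.0 / 59.0 |
| 0.5 | 75.6 / 59.5 | 86.8 / 75.8 | 86.3 / 75.2 |
| 0.68 | 75.4 / 58.7 | 89.9 / 79.3 | 91.0 / 83.0 |
| 0.75 | 75.2 / 58.1 | 91.2 / 80.9 | 92.9 / 86.4 |
| 0.8 | 75.0 / 57.6 | 92.2 / 82.2 | 94.2 / 88.9 |
| 1 | 74.0 / 54.5 | 96.4 / 87.9 | 100 / 100 |

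**True deficit.** An uncorrected independent interval with Unassisted 0.5 to 0.6 points lower gives 92.6% / 83.1% to 91.7% / 82.0%. The named interval with a 1-point deficit and uncorrelated periods gives 55.8% / 44.6% (1/30) or 63.2% / 57.1% (1/60).

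**Analysed number** (independent, no difference). Power moves in steps. The 1/n form gives about 76% / 60% at n = 28, 75% / 59% at 30 and 95% / 84% at 37. The 1/(2n) form gives about 81% / 71% at 28, 80% / 70% at 30 and 96% / 87% at 32.

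**Premise for the independent analysis.** P(no Assisted failure in 30) = 0.99³⁰ = 74.0%, or 0.98³⁰ = 54.5%.

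**The case against.** The strongest reply is that zero correlation is not the protocol's assumption. The same subjects supply both periods, section 9.4.2 calls the rates paired, and a positive correlation in dialysis adequacy is plausible. With the 1/60 form and a correlation of 0.8, the named interval gives 92.2% / 82.2%, within simulation error of the stated pair. This stands: the named interval can yield roughly those figures, so the mismatch must be stated with its conditions. But no correlation is documented, about 0.7 to 0.8 is needed to come near, and the 1/30 form stays at about 74-76% / 55-60% whatever the correlation.

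Second, another method or scenario may have been simulated. A paired Wald interval with 1/30 correction at correlation 0.68 gives exactly 91.0% / 83.0%, and an uncorrected interval with a small deficit also comes close. This also stands, and it rules out calling the simulation wrong. The quoted power would then belong to an analysis other than the one section 9.4.2 names.

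Third, an SAP may fix the correction, and the position of the corrected analysis after the ITT imputation paragraph makes its primary role partly an inference. That is fair, but no other interval is offered and the same analysis is then applied to the PP set.

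Fourth, 99% and 98% are two cases from a simulated range of 95% to 99.5%; at 99.5% the chance of no Assisted failure is 0.995³⁰ = 86%. That softens the criticism of the no-failure premise without touching the power statement. The sample size is also unaffected, because the 30 subjects follow from the 1,000-treatment goal.

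**Conclusion.** The concern holds. At n = 30, with no true difference and uncorrelated periods, the named interval misses the endpoint with probability of about 25% / 41% (1/30) or 20% / 30% (1/60) at 99% / 98% success. The stated power implies 9% / 17%. Positive correlation narrows the gap for the 1/60 form only. The open choice of correction reverses the verdict when each period has one failure, an outcome with probability 5% / 11% if periods are independent (0.2242² and 0.3340²). The conflict between the synopsis and section 9.2 over the simulated difference needs no calculation and no assumption. The documents do not show how 91% / 83% was obtained, so the conclusion is limited to a mismatch between stated power and planned analysis. It should be fixed before data are seen.

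**What to change.** - In section 9.4.2, name one primary interval and the exact form of its continuity correction. If the SAP fixes the form, cite it there.
- In the synopsis and section 9.2, describe one and the same simulation: true difference, within-subject correlation and interval.
- Re-run it for the planned interval and restate the power. At n = 30 with independent periods and no difference, expect about 75% / 59% (1/30) or 80% / 70% (1/60). Any higher figure that rests on a correlation should state and justify it.
- If a paired interval was simulated, say so, and either plan that interval or replace its power figure.

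The cost is protocol and SAP wording plus one re-run of the simulation, with no extra patients. The downside is a less favourable stated power, unless a within-subject correlation or a larger analysed number can be justified.
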